Table 1. Trusts providing home based and / or day hospital rehabilitation. Forty six percent of trusts responding to the first contact questionnaire reported providing both types of service.

2nd contact questionnaire					
	Home based		Day hospital		
Replies received	150		114		p-value
SERVICES	n	%	n	%	
Fn Assessment	115	77%	108	95%	<0.01
Medical assessment	53	35%	102	90%	<0.01
Rehabilitation	103	69%	94	83%	<0.01
Respite & Social Care	45	30%	32	28%	>0.2
Specialist medical assessment	33	22%	69	61%	<0.01
Nursing procedures	87	58%	104	91%	<0.01
Specialised Stroke	61	41%	76	67%	<0.01
Specialised TIA	35	23%	61	54%	<0.01
PD	45	30%	74	65%	<0.01
Movement disorders	31	21%	49	43%	<0.01
Falls	69	46%	91	80%	<0.01
Continenence	50	33%	50	44%	>0.05
Physical maintenance	34	23%	43	38%	<0.01
STAFF					
Other	77	51%	75	66%	<0.05
Community Nurse	65	43%	18	16%	<0.01
GP	32	21%	21	18%	> 0.1
Hospital nurse	11	7%	62	54%	<0.01
Hospital Doctor	14	9%	70	61%	<0.01
OT	103	69%	99	86%	>0.2
PT	100	67%	97	84%	>0.2
Therapy assistant	88	59%	81	70%	>0.2
Admin staff	63	42%	82	71%	>0.2
Other	59	39%	54	47%	<0.05
Time limited service	75	50%	54	47%	>0.2

(P-value refers to the significance of the difference in provisions between home based and day hospital service (chi))

Table 2. Results of 2nd contact questionnaire received from trusts providing home based and / or day hospital rehabilitation. Note that day hospitals are very much more likely to provide medical or specialised medical services and, home based services are more likely to be provided by community practitioners (GP and Nurse).

b). Pilot work in 3 Trusts to prepare for the RCT

We have piloted the research in 3 trusts, to enable us to establish and resolve practical difficulties in conducting the trial.

Methods

Ethical approval was sought and granted to work in 3 sites, Sheffield, Barnsley and North Tyneside, using both day hospital and home based rehabilitation services. It was agreed that a pre-pilot was necessary, the main purpose being to test out the length and difficulty of the economic questionnaire which had been developed from that used in a RCT on cardiac pace making of older people at CHSR, University of Newcastle, and the Northern Region Day

Hospital Audit (NRDHA). 10 Pre-pilot interviews were done with day hospital rehabilitation patients in Barnsley.

Pre-pilot Interviews

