Patients referred for rehabilitation will be routed through a central point. They will be assessed for their need for rehabilitation and the assessor will complete the Oxford Handicap Scale and Abbreviated Mental Test. The patient will be informed of the research using a Patient Information Sheet. If the patient consents to research they will be randomised to home based or day hospital rehabilitation following a baseline interview, using computer generated block randomisation within each centre, managed by an independent member of the research team and available during the normal opening times of conventional day hospital services. Feasibility of randomisation has been explored with professionals working in pilot and potential trial sites, and while there were some concerns there was a level of understanding about the necessity of randomisation. Time for piloting randomisation processes is built in to the running time in each site to accommodate local issues, and in the first sites to begin randomisation an initial period of piloting will test and resolve any problems in procedures. The scoping study will have identified variation between sites on a number of key variables (e.g. age distribution, range of clinical conditions, sources of referral), which will inform a final decision about stratification. Eligible patients will be stratified by source of referral (hospital inpatient or primary health care team) and the Oxford Handicap Scale using a cut point of 2/3. It is possible that patients will be referred for rehabilitation more than once in the course of the year that they are part of the research. Subjects re-referred to the trial will continue treatment in the arm of the trial to which they were first randomised and study follow-up will continue from the point of randomisation.

Informing GPs about the research

Prior to patient recruitment we will inform all GP surgeries local to the trial site about the research. As patients are recruited we will inform their GP's individually that they are a participant in the trial and that we will contact the GP prior to contacting the patient for follow-up, to check for death.

Outcome measures

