Outcomes will be assessed by interview but in addition (to assess potential bias due to ineffective blinding of interviewers) self-completed questionnaires will be completed by a randomly selected 50% of surviving subjects at 6 months and by the other 50% at 12 months. The primary outcome will be functional health status as measured using the Nottingham Extended ADL scale¹³. All outcomes will be measured at base line and at 3, 6 and 12 months after recruitment by interviewers who are unaware of the treatment allocation (see below). Carer interviews will take place within 1 month of patient interviews. Secondary outcome measures will include survival (death certifications) and changes in subject's perceived mental state (Hospital Anxiety and Depression Scale⁽¹⁴⁾), change in household or residential or nursing home circumstances (study records), informal caregiver's psychological health (General Health Questionnaire (GHQ)⁽¹⁵⁾) and patient's and informal caregiver's views of 'treatment' (semi-structured interviews). Therapy Outcome Measures (TOMS) will be used to measure outcomes in relation to rehabilitation aims.

Assessment of quality of life is implicit within the choice of outcome measures, (including EuroQOL). No generic and comprehensive quality of life measure is proposed since there is no evidence that a suitable measure exists for this particular patient group. Taken together the proposed outcome measures cover the traditional domains of quality of life included in generic measures. In the absence of reliable patient reported data, data collected from informal caregivers will be substituted where appropriate since previous studies have indicated that informants are a source of reliable data^(16 17 18). The applicants have used all the proposed outcome measures identified in recent studies and found them to be appropriate to the study.

Patient Interviews

Patients will be interviewed in their own homes, following prior arrangement by telephone or letter, by a researcher unaware of their treatment allocation. The interviews have been shown in the pilot to take between 30 minutes to an hour. Patients' welfare will be considered of paramount importance at all times. Proxy information will be used if the interviewer feels that the patient is not capable of answering questions accurately. This will be judged by a combination of AMT score and ability to answer pre-interview questions. The interview will

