Analysis of the trial data will be on an 'intention to treat' basis. Univariate and multivariate techniques including survival analysis, non-parametric analysis of variance and log-linear modelling will be used to evaluate the relationships between inputs and outcomes. Interim analysis of throughput, case mix and difference in primary outcome will be done by an independent data monitoring committee 9 and 21 months after recruitment has begun (at the end of the first and second year of the study). We will monitor throughput but all other analysis will wait until the end of data collection.

Economic Evaluation

Perspective of the study

An economic evaluation will be conducted alongside the clinical trial to compare home-based rehabilitation (HBR) vs. day hospital rehabilitation (DHR). DHR is considered to be the current practice. The aim of the study is to test the hypothesis that for older people requiring rehabilitation, HBR: (i) is not less effective than DHR, (ii) is not less preferable than DHR to the patients and their carers, (iii) is less costly than DHR.

The economic evaluation will address the study question from the NHS decision making and societal perspectives (20). We recognise that a decision making perspective is particularly suitable to address the study questions posed by the NHS research programme. However, we believe the societal perspective to be also important because the problem under investigation has an impact on other agents beyond the health service, and the decision maker may want to be informed about such implications.

The societal perspective is aimed at including all costs and health effects regardless of who incurs the costs and who obtains the benefits (21). We will try to make the collection of the most important data to address the societal perspective practically feasible, without making the data collection instruments too cumbersome. Therefore, we will consider the costs (and benefits) to the providers of health and social services, the patients and their carers. Although a wide range of cost items and outcomes will be included, the core analysis will focus on the subsets of costs and effects relevant for allocating the health service budget.

Measures of benefits used and study type

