therapy, speech therapy, nursing, medical assessment and intervention, and transportation costs of patients/carers to and from day hospital centres; and of health care professionals to and from patients' homes; use of special aids and equipment; introduction of home alterations; personal care received through rehabilitation service. The provision of social and personal services which do not contribute directly to the rehabilitation process is excluded from the evaluation of these packages of care. However, they will be considered within the economic evaluation:

Information on personal and social services received at home will be collected through interviews (see below); information on personal and social services provided in day hospital will be monitored in each centre.

To estimate the use of resources made by the rehabilitation team, service elements will be recorded for each patient in a proforma. These will include date of visits, job title of the health care professional(s) seen on that day, the grade, the length of visit, the mileage per patient. The total time per patient will be the time spent on all service elements for that patient. This will allow to estimate labour costs. All material items/ equipment used during each action will be also be recorded. Fixed costs, such as overheads and general costs will be allocated pro-rata according to relevant parameters such as floor area used, number of staff, throughput.

Estimation of subsequent use of resources. Use of services - other than those included as part of the packages of care - to be monitored in both patient groups via questionnaire include: outpatient visits and hospitalisations, investigations, A&E admissions, use of ambulance services, visits and telephone consultations to and from the general practitioner and any other health care professionals, use of medications, personal and social services, attendance to day care centres, short-term respite or permanent care.

Details on procedures/investigations undertaken in hospital (eg, during hospitalisation or casualty attendance) will be extracted from patients' records, at 3, 6, 9, 12 months post-randomisation, as well as being including in questionnaire, to double check. Records will be reviewed over the previous three months.

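### The data monitoring committee's interim list omits deaths and hospital admissions by arm, so an imbalance would get no formal review before the end of the trial

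*Protocol*

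**What the plan says.** The Analysis section under Phase 2 gives the committee's task as a list of three items: "Interim analysis of throughput, case mix and difference in primary outcome will be done by an independent data monitoring committee". The looks are set at "9 and 21 months after recruitment has begun (at the end of the first and second year of the study"). The next sentence reads: "We will monitor throughput but all other analysis will wait until the end of data collection".

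The third item is NEADL, since the Outcome measures section states: "The primary outcome will be functional health status as measured using the Nottingham Extended ADL scale". Survival is a separate outcome there: "Secondary outcome measures will include survival (death certifications").

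Vital status is gathered while the trial runs. Under Informing GPs about the research, the protocol says "we will contact the GP prior to contacting the patient for follow-up, to check for death". Admissions are gathered too, for the economic evaluation. Under Resource data collection and costing methods, the services "to be monitored in both patient groups via questionnaire include: outpatient visits and hospitalisations, investigations, A&E admissions".

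**The concern.** The committee is the only body that the protocol names to see comparative data during the trial. Read as written, it sees how many patients have been recruited, what kind of patients they are, and the difference in NEADL. Deaths and admissions, the events most directly linked to harm in a population expected to be about 90% over 70, are not on the list.

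The omission matters for this comparison in particular. The caption of Table 2 in the national survey notes that "day hospitals are very much more likely to provide medical or specialised medical services". The table gives medical assessment in 90% of day hospitals against 35% of home services, nursing procedures in 91% against 58%, and a hospital doctor in 61% against 9%. If less medical input did harm, deaths and admissions are where one would look first. The trial's hypothesis is that patients do not lose out under home rehabilitation.

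There is a second, smaller issue. NEADL is obtained by interview, and the GP check removes patients who have died before the interviewer makes contact. The protocol does not say how a death counts on NEADL. If the interim comparison uses only those interviewed, an arm that loses more of its frailest patients shows a higher mean for that reason alone.

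**Working it through.** **1. What is routed to the committee**

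| Item | Collected during the trial? | On the committee's list? |
|---|---|---|
| Throughput, case mix | Yes | Yes |
| NEADL | Yes, at 3, 6 and 12 months | Yes |
| Deaths | Yes, GP check before follow-up contact | No |
| Admissions | Yes, questionnaire | No |

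No other section provides for adverse-event review or for a comparison of deaths by arm before the end. The omission needs no arithmetic. The steps below size its consequences.

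**2. Implied SD.** The Sample size section gives 230 per arm, a 2-point difference, 90% power and a 5% level, but no SD. Taking the level as two-sided (assumed):

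SD = 2 / [(1.960 + 1.282) × √(2/230)] = 6.62.

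This is back-solved, so it reproduces the 460 by construction and is not an independent check of it.

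**3. Distortion of a survivors-only NEADL difference.** Assume the same underlying function in both arms, normally distributed, with deaths linked to low function by a correlation ρ. If a fraction p dies, the survivors' mean rises by ρ × SD × φ(z_p)/(1 − p). The factor φ(z_p)/(1 − p) is 0.195 at p = 0.10 and 0.274 at p = 0.15. For an assumed 10% v 15% mortality:

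- ρ = 1 (worst case): 6.62 × (0.274 − 0.195) = about 0.52 points.
- ρ = 0.25: about 0.13 points.

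The protocol gives neither mortality rates nor ρ, so the range over assumptions (ρ from 0.25 to 1) is:

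| Mortality (assumed) | SD 6.62 (implied) | SD 15 (assumed) |
|---|---|---|
| 10% v 15% | 0.13 to 0.52 | 0.30 to 1.19 |
| 10% v 20% | 0.26 to 1.03 | 0.58 to 2.32 |
| 5% v 10% | 0.14 to 0.57 | 0.32 to 1.30 |

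**4. Who could be counted at month 9.** The Recruitment section assumes six sites opening every two months, each with 50 patients per arm per year, or 100/12 = 8.33 patients a month.

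- Randomised: (9 + 7 + 5 + 3 + 1) = 25 site-months × 8.33 = 208, or 104 per arm.
- Past 3 months: (6 + 4 + 2) = 12 site-months × 8.33 = 100, or 50 per arm.
- Not yet at 3 months: 208 − 100 = 108.

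The same section starts at the smallest site, so the early numbers are probably lower.

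**5. Power for mortality at each look.** By month 21 the same plan gives (21 + 19 + 17 + 15 + 13 + 11) = 96 site-months × 8.33 = 800, so the target of 680 (340 per arm) would be full. Two-sided 5% power for assumed 12-month mortality:

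| Mortality (assumed) | 104 per arm | 340 per arm |
|---|---|---|
| 10% v 15% | 0.19 | 0.50 |
| 10% v 20% | 0.52 | 0.96 |
| 5% v 10% | 0.28 | 0.70 |

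These credit every patient with a full 12-month risk, so they are upper limits at both looks.

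**The case against.** Several points on the other side are sound.

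- **The deferral sentence does not bar the committee.** A reader might infer from "We will monitor throughput but all other analysis will wait until the end of data collection" that survival is withheld from everyone. Its subject is the trial team, and applied to the committee it would contradict the sentence before it. What remains is an item left off a list, not a prohibition. A committee charter, not shown, could add deaths.
- **Deaths would not be hidden.** A reader might infer that excess mortality would go unnoticed. The GP checks mean that individual deaths are known to the research team. What is missing is a formal comparison by arm.
- **Prior evidence is partly reassuring.** The systematic review in the Literature section thought a day hospital advantage in mortality or bed use unlikely. The Table 2 contrasts come from all survey respondents, and few potential sites met the criteria on throughput and range of services, so the contrasts may not describe the trial's arms. Against this, the same review says the day hospital has not been adequately evaluated as a setting and that home rehabilitation trials were condition-specific.
- **The NEADL distortion is easily overstated.** Removing the lowest 5% from one arm and nobody from the other gives about 0.72 points, over a third of the target. That compares 5% mortality with 0%. With 10% mortality in the comparator, the same worst case gives 0.52. It also needs a survivors-only analysis, which is an inference.
- **The data are not all in hand.** GP checks are tied to follow-up, and outcome follow-up starts at 3 months. About 108 of 208 patients at month 9 would not have reached it. Reported admissions rest on patient recall over one month (Resource data collection) or eight weeks (patient economic questionnaire).
- **The looks have limited reach.** Power at month 9 is low. On the planned accrual, recruitment would finish at about month 19, from (6t − 30) × 8.33 = 680, giving t = 18.6. With 95% of patients expected to be discharged within 16 weeks, little treatment would remain at the second look.

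These points limit the size and the wording of the concern. None of them puts deaths or admissions in front of the committee, and low power is a reason to read the counts with care, not to leave them out.

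**Conclusion.** The omission stands on the protocol's text: the committee's list leaves out deaths and admissions by arm, and no other section arranges that comparison before the end of the trial. An imbalance would not be formally reviewed, even though the team knows of individual deaths.

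The effect on the interim NEADL reading is conditional and modest. It is about 0.1 to 0.5 points against the 2-point target, resting on the implied SD of 6.6, an assumed 10% v 15% mortality, assumed frailty correlations of 0.25 to 1, and a survivors-only comparison. It reaches 2 points only in an extreme case (assumed SD 15, 10% v 20%, perfect correlation).

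The documents do not show that a harmful arm would look beneficial, or that the committee is forbidden to see deaths. This is a cheap improvement to patient safety monitoring. It does not challenge the sample size or the final analysis.

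**What to change.** In the Analysis section:

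1. Add to the committee's items at 9 and 21 months: deaths by arm among all randomised patients, as known at the report date from GP checks and death certification, and hospital admissions by arm from the data already collected.
2. Have the interim NEADL difference shown with the numbers interviewed and the numbers dead in each arm.
3. State that the deferral of all other analysis applies to the trial team and not to the committee's confidential reports.

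The cost is a little more work for whoever prepares the committee's reports and possibly some extra vital-status checks for patients not yet at 3 months. The sample size does not change. The committee should be told that the first look has limited power for mortality, at most about 0.5 for an assumed 10% v 20%, so the absence of a clear difference there would not be reassurance.

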Additional	Need identified for holistic goal related measurement (see section 4.3.3.3)	Therapy Outcome Measures (12) See appendix 10.
	No specific provision	Semi structured Interview for determining patient and carer views of treatment.

Table 5. Changes to research instruments.

Feedback:

- The current policy environment continues to stimulate change in healthcare provision in the area, and the results of this trial will be informative in evidence-based policy making.
- Our methodology may not be sensitive to key differences between the 2 groups at the level of achieving rehabilitation goals.. When the protocol was originally proposed there was no practical research tool which would take into account the aims of rehabilitation. Goal Attainment Scaling was available but time consuming for professionals and researchers. Since this time, Therapy Outcome Measures has been validated with this patient group, therefore will be included. TOMS is based on observations of the goals of therapy and aims to provide a reliable and valid way of collecting data for the purpose of outcome measurement. It is administered by rehabilitation staff, who will be trained in it's use.

Protocol modifications suggested by Phase 1 data.

The Trial Management Group has met to consider findings of Phase 1 and the implications of this to Phase 2. Table 2 outlines the main changes to the protocol which the trial management team believe are suggested by the pilot work

Key Finding	Original Protocol	Recommendation
There is considerable heterogeneity between potential trial sites which is independent of the urban / rural setting. Less than 10% of potential trial sites satisfied explicit inclusion criteria based on throughput and range of services.	3 trial sites, 460 patients (after allowing for attrition and non-response).	6-8 trial sites, with a smaller number of patients in each site, to better represent the range of services provided. Total sample size remains the same.
The majority of sites with co-incident day hospital and home based rehabilitation services report ongoing or imminent changes to their service. This suggests that previous descriptive work is likely to be, or soon to become out of date.	Not addressed.	Add-on contextual study. A descriptive analysis of service models and processes across a range of sites will be essential to accurately contextualise the findings of a contemporaneous trial.

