Costing methods: Costing of health and social care will be undertaken in a parallel study and a mixed approach using microcosting and gross costing methods will be used(24). The perspective used in the study affects the way in which resources have to be costed (25). Generally, resources should be valued at their (marginal) opportunity costs, and market prices are usually used as a proxy measure. We will cost resources using national average cost figures (26);(27);(28). We expect scarcity of published cost data in relation to rehabilitative care. Whenever necessary, cost estimation procedures will be developed and local NHS and social service accounting figures will be used to estimate total costs. Then, two methods of costing will be used and compared as suggested by the methodological literature(29): at first, unit costs averaged across centres will be applied to centre-specific volume of resources used; therefore, these results will be compared with those obtained using centre-specific information for both the unit costs and the resources volumes, and averages across centres will be calculated. Where relevant, costs will be broken down into capital, staff, consumable and overhead costs. This will aid the production of different cost scenarios, and the understanding of the implications on the marginal cost evaluation.

Other costs to carers: The impact of the interventions on carers' daily activity and their use of time will also be monitored. Informal carers will be identified through the patients' interviews.

Questionnaires will be interview administered up to one month after the patients' interview, to allow adequate time to identify, locate and contact the carers.

For carers in paid/unpaid work (eg. doing housing or voluntary work), time will be valued in monetary terms. Carers' lost leisure time will also be measured. However their impact will be assessed through HRQoL instruments(30), and therefore will not be valued in monetary terms.

Methods of data analysis

Average total costs between groups will be compared at the time points of data collection, in relation to the outcome results. Costs will be expressed in UK pounds sterling. No conversion to other currencies will be made. Costs will be expressed in the prices of the year in which the final analysis will be carried out and inflation method will be used to update costs data. Given the length of follow-up period, no discounting will be necessary.

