We expect skeweness in the distribution of use of resources/costs(31). In the presence of skeweness, the logarithmic transformation of data is not recommendable, and the application of non-parametric tests can provide misleading results (in fact economic studies should aim to base the analysis on arithmetic means and not median values) (32);(33). The non-parametric bootstrap test can be the most appropriate (34), since it does not require any assumptions about the normality of data and equality of the variance or shape of the distributions. The t-test can be safely used if the sample size is not too small (33). Therefore, depending on the level of skeweness of data we will obtain and our sample size, we will make a judgement on which of these two methods can be safely applied.

Synthesis of costs and benefits

Summary results will be presented in aggregate and for each sub-group of analysis (groups will be defined in terms of severity and functional disability). Depending on the outcome measure, if there will not be evidence that one strategy is more effective than another, a cost-minimisation framework will be used and the less expensive form of care expressed in terms of cost per patient will be recommended. If one strategy appears to be dominant (ie. to be more effective and less costly than the alternative), its' uptake will be recommended. If one form of care appears to be more effective and more expensive than the comparator, the results of the study will provide useful information, and a judgement will be required in a decision making context to establish whether the additional benefits should be achieved sustaining the additional costs. In any case, recommendations will be made taking into account of the generalisability of the results. Incremental costs will be calculated overall and in relation to any reduced use of services included in the packages of care.

Sensitivity analysis

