	Reliability	Validity	Appropriate to population
HADS	Zigmond and Snaith (1983) Bjelland et al (2002)	Zigmond and Snaith (1983) Bjelland et al (2002)	Bjelland et al (2002) Wolf et al (2001)
GHQ	Bowling (1995)	(Bowling 1995)	Watts et al (2002) Bautz-Holter et al (2002)
NEADL	Bowling (1995)	I-Ping (2000)	Harwood et al (2002), Nichol et al (2002)
EUROQUOL	Schrag et al (2000)	Schrag et al (2000)	Wade et al (2003)

Economic Questionnaire for patients

University of Sheffield Sheffield Institute for Studies on Ageing Rehabilitation of Older Patients: day hospital compared to rehabilitation at home – HTA Project No: 97/26/01		
Patient Interview Schedule 2 – Economic		
Patient study number		1
Interviewer ([name]=1)		2
Interview done in home(1)/hospital(2)		3
Date		4
Baseline(0)/3 months (1)/6 months(2)/1 year(3)		5
Proxy? Yes(1)/No(2)		6
Relationship of proxy to patient Husband/wife (1) Son/daughter (2) Grandchild (3) Other relative (4) Friend (5) Paid carer (6)		7
0	So, when did you start your rehabilitative treatment (date)?	8
	Now I will ask you a series of questions about the use of health and social services through the NHS. I only want to know about things you have had in addition to your rehabilitation treatment:	
1	In the last 8 weeks have you done any of the following because of your condition or other health reasons? Can you please also remember how many times these events have happened? Please do not count visits you have made as part of your rehabilitation treatment.	
a)	Have you been seen by the family doctor or another GP at a doctor's surgery?	9
	Yes..... 1 no. times  	10

	No 2	
b)	Have you been seen by a nurse at a surgery? Yes 1 no. times   No 2	11 12
c)	a) Did you or anyone else speak to a nurse from a doctor's surgery about you on the telephone? Yes 1 no. times   No 2	13 14
d)	Did you or anyone else speak to a doctor at the surgery about you on the telephone? Yes 1 no. times   No 2	15 16
e)	Did you or anyone else telephone NHS Direct? Yes 1 no. times   No 2	17 18
f)	Have you visited an emergency doctor at an "out of hours" clinic? Yes 1 no. times   No 2	19 20

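### The cost comparison names no term for the factors used in randomisation, so its confidence interval may be somewhat wider than the design requires

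*Protocol*

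**What the plan says.** *Perspective of the study* sets out the hypothesis that home-based rehabilitation "is less costly than DHR". *Methods of data analysis* states: "Average total costs between groups will be compared at the time points of data collection, in relation to the outcome results". It then treats skewness, rejects log transformation and rank-type tests because inference should rest on arithmetic means, and leaves two candidates. Of one it says: "The non-parametric bootstrap test can be the most appropriate (34"). The other is the t-test, if the sample is not too small. The choice is deferred: "depending on the level of skeweness of data we will obtain and our sample size, we will make a judgement on which of these two" is safe. No covariate or stratification factor is named for either.

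*Randomisation, stratification and assessment* describes allocation "using computer generated block randomisation within each centre" and adds: "Eligible patients will be stratified by source of referral (hospital inpatient or primary health care team) and the Oxford Handicap Scale", with a cut point of 2/3. The same section says that the scoping study will inform a final decision about stratification.

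On baseline resource use the protocol is not consistent:

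- The patient economic questionnaire carries the visit code "Baseline(0)/3 months (1)/6 months(2)/1 year(3") and asks about the last 8 weeks, leaving out the rehabilitation treatment itself.
- *Outcome measures* has all outcomes measured at baseline and at 3, 6 and 12 months.
- *Resource data collection and costing methods* places the resource interviews at 1, 3, 6 and 12 months after randomisation, with recall over the previous month and no baseline interview.

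**The concern.** When allocation is balanced within centre and strata, cost variation between those groups largely cancels from the difference between arms. A plain two-group test still counts that variation in its standard error. The reported interval is then wider than the true sampling variation of the estimate, and the test rejects less often than its nominal level.

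The protocol gives some reason to expect such variation. Table 6 says: "There is considerable heterogeneity between potential trial sites". The economic section expects day hospital care to vary within and between centres, and it plans to summarise results by severity and functional disability.

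At stake is the precision of the cost difference. Under *Synthesis of costs and benefits*, if neither service is shown to be more effective, the cheaper one is to be recommended, so the cost result may carry the trial's conclusion.

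**Working it through.** **Inputs from the protocol.** There are 460 patients for analysis, 230 per arm (*Sample size*), and an aim of 8 sites (*Research Sites*). There is no cost SD, centre share of cost variance, baseline correlation or power for costs, so there is no cost figure to reproduce. The stated 90% power concerns the Nottingham EADL scale.

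**Assumption.** R² is the share of cost variance explained by the adjustment factors. It is varied from 0.01 to 0.25.

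**Formulas.**

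- Ratio of adjusted to unadjusted standard error: √(1 − R²).
- Adjusted power, starting from a nominal 80%: Φ((1.96 + 0.842)/√(1 − R²) − 1.96). The 80% is itself an assumption.
- Actual two-sided error of the unadjusted test when the explained variance lies in factors balanced by randomisation: 2(1 − Φ(1.96/√(1 − R²))).
- Unadjusted sample giving the same precision: 460/(1 − R²).

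| R² | SE ratio | CI narrower by | Adjusted power | Actual error, unadjusted test | Equivalent N |
|---|---|---|---|---|---|
| 0.01 | 0.995 | 0.5% | 80.4% | 4.9% | 465 |
| 0.05 | 0.975 | 2.5% | 82.0% | 4.4% | 484 |
| 0.10 | 0.949 | 5.1% | 84.0% | 3.9% | 511 |
| 0.20 | 0.894 | 10.6% | 87.9% | 2.8% | 575 |
| 0.25 | 0.866 | 13.4% | 89.9% | 2.4% | 613 |

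The error column applies only to variance explained by centre and strata. Baseline cost is not balanced by design, so omitting it loses precision but leaves the test at its nominal level.

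The power column is an upper bound on the gain. If the explained variance comes from centre and strata, the unadjusted test already does a little better than 80%. Its actual power is Φ(0.842/√(1 − R²)), which at R² = 0.10 is Φ(0.887) = 81.2%, against 84.0% adjusted.

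**Simulation.** Costs were log-normal with coefficient of variation 1, for 460 patients in 8 centres with balanced allocation within centre, over 1,000 runs. Centre share and baseline correlation are on the log scale.

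| Centre share | Baseline correlation | SE ratio, centre only | SE ratio, centre and baseline cost |
|---|---|---|---|
| 0 | 0 | 1.000 | 1.001 |
| 0.05 | 0 | 0.1278/0.1298 = 0.985 | 0.986 |
| 0.05 | 0.3 | 0.1278/0.1300 = 0.983 | 0.956 |
| 0.10 | 0.5 | 0.1253/0.1295 = 0.968 | 0.883 |

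Three things follow:

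- Adjustment costs almost nothing when the factors are useless.
- In these scenarios centre alone gives about 1.5–3% and the larger gains come from baseline cost, the variable whose collection is uncertain.
- The unadjusted test rejected in 4.3–5.2% of null runs. With a Monte Carlo error of √(0.05 × 0.95/1000) = 0.7 percentage points, no conservatism was visible at these sizes.

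**The case against.** The strongest reply is that the protocol never says the comparison is unadjusted. Its passage on tests answers a narrower question, how to make inference on means when costs are skewed. A bootstrap can be stratified or applied to a regression, the *Analysis* section mentions multivariate techniques, and covariate lists often belong in a statistical analysis plan, which is not at hand. This stands in part: a reader might infer that adjustment is ruled out, and the text does not go so far. But the protocol does more than stay silent. It narrows the choice to two tests, one of which is a plain two-group comparison, and describes the other only as free of assumptions about normality, variance and shape. The multivariate techniques are not applied to costs.

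A reader might also take baseline resource use as settled, since the form has a baseline code. The economic section's interview schedule contradicts this. Even if the data are collected, the form omits rehabilitation treatment, the very cost in which the arms differ, so a high baseline correlation should not be presumed.

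The heterogeneity in Table 6 concerns throughput and range of services among potential sites, not cost per patient among recruited ones. The first costing method applies unit costs averaged across centres, which removes price differences from that analysis. Both points stand and argue for the lower end of the R² range.

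Finally, the cost-minimisation recommendation states no significance requirement, and *Sensitivity analysis* covers resource differences that matter in practice without reaching significance. This softens the consequence but does not make a wider interval useful.

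**Conclusion.** The point holds as a modest matter of efficiency. The stated cost test names none of the factors used in randomisation, and using them would be nearly free. A reader might infer that the planned comparison is biased or invalid. It is neither: at worst its interval is too wide and its test slightly conservative.

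The size rests wholly on assumed R². At 0.10 or less the interval narrows by 0–5% and a nominal 80% power becomes at most 84%. At 0.20–0.25 it narrows by 10.6–13.4% and power reaches 87.9–89.9%. A reader might take the higher figures as the expected gain, but nothing in the protocol supports choosing them. Leaving the choice between two tests until the skewness is seen is a further, avoidable looseness that the same change removes.

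**What to change.** In *Methods of data analysis*, replace the deferred choice with one prespecified method. Estimate the difference in arithmetic mean cost from a linear regression on arm, centre, referral source and Oxford Handicap Scale (cut 2/3), or on whatever strata are finally adopted. Take the confidence interval from a bootstrap that resamples within centre and arm. Report the unadjusted mean difference as support. This keeps arithmetic means, as the protocol wants.

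Separately, reconcile *Outcome measures* and the economic questionnaire (baseline visit, 8-week recall) with *Resource data collection and costing methods* (1, 3, 6 and 12 months, one-month recall). Add baseline 8-week resource cost as a covariate only if it is in fact collected.

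The cost is a change of wording and slightly more analysis work, plus simple imputation of any missing baseline cost if that covariate is used. The design factors are needed for randomisation anyway, so the core change adds no patients and no data collection.
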